To determine the tolerability of low residue diet for colonoscopy bowel preparation in special populations (elderly, diabetes mellitus, chronic kidney disase, chronic liver disease) versus clear liquid diet.

Review of Related Literature

CRC screening in average-risk persons should begin at age 50, except that in African Americans, screening should begin at age 45 years. A family history of polyps need not invoke earlier onset of screening or other adjustment in screening, unless there is convincing evidence that the polyps were advanced adenomas. [8]. Given the finding that adenomatous polyps are precursors to cancer and that polyps and early cancers are usually asymptomatic, there is a

strong rationale to support screening asymptomatic individuals for early cancer detection and prevention. [3]

Colonoscopy is the current standard method for imaging the mucosa of the entire colon. Large-scale reviews have shown rates of incomplete colonoscopy, defined as the inability to achieve cecal intubation and mucosal visualization effectively, between 10% and 20%, well over targets recommended by the U.S. Multi-Society Task Force on Colorectal Cancer.[6]

The diagnostic accuracy and therapeutic safety of colonoscopy depends, in part, on the quality of the colonic cleansing or preparation. Inadequate bowel preparation can result in failed detection of prevalent neoplastic lesions and has been linked to an increased risk of procedural adverse events. [6]

In clinical practice, preparation quality should be graded after efforts to remove residual effluent and fecal debris have been completed. Validated scoring systems that have been devised to rate the quality of colonoscopy preparation in clinical trials include the Aronchick Scale, the Ottawa Bowel Preparation Scale, and the Boston Bowel Prep Score .[5]

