Baseline characteristics of the patients will be described as mean and standard deviation among continuous variables while percentage will be utilized for categorical data. In comparing the two groups, t-test will be used to compare means such as BBPSscore, while chi square test will be utilized for categorical variables such as proportion of adequate bowel preparation. All significant test will be done at 5 % level. A non inferiority margin of 0.05 was set. Medcalc statistical calculator will be utilized to carry out statistical computations.

Results

Patients Demographics

A total of 75 patientseach from low residue diet and clear liquid diet group were included in this study whose average age is 67.9 and 64.9 respectively (p=.0515). (Table 1). It also showed that around 82.7% of the patients in low residue are elderly, which is not significantly different from the resulting proportion of elderly patients in clear liquid diet group (72%). (Table 1) Moreover, both group is composed mostly of male (61% vs 75%, Low Residue vs Clear liquid), while proportion of occurrence of diabetes mellitus, chronic kidney disease and chronic liver disease is also not significantly different for the two groups.(Table 1). There were also no differences in terms of cecal intubation rate, withdrawal time, out patients and in patient's number.(Table 1).

Table 1. Patient Baseline Demographic Information

Profile	Low Residue Diet (n=75)	Clear Liquid Diet (n=75)	p value
Age (years), mean±sd	67.9 ± 9.5	64.9 ± 9.0	0.0515 ^{ns}
Elderly (>60), n,%	62 (82.7)	54 (72.0)	0.1200 ^{ns}
Sex, n,%			
Male	46 (61.3)	56 (74.7)	0.0811 ns

Female	29 (38.7)	19 (25.3)	
Comorbidities, n,%			
Diabetes Mellitus	32 (42.7)	29 (38.7)	0.6192 ns
Chronic Kidney Disease	11 (14.7)	6 (8.0)	0.1993 ns
Chronic Liver Disease	5 (6.7)	5 (6.7)	1.0000 ns
Others			
Cecal intubation rate	75 (100)	75(100)	1.0
Withrawal time	8.6±2.2	8.95±2.5	0.3642
In patients	44(58.7)	39(52)	0.4131
Out patients	31(41.3)	36(48)	

Adequacy of Bowel Preparation

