The proportion of patients who developed nausea and vomiting were not statistically significant between the two groups(5.35 vs 12 %,p=0.148)(Table 3a). However, the occurrence of abdominal pain/cramping/discomfort (34.7%) and bloatedness (44%) are significantly higher in clear liquid diet group compared to low residue diet group(16% and 26.7% respectively, p=0.0088 and0.0269) (Table 3a). Moreover, patients in the LRD group were less hungry before colonoscopy as compared to CLD group(4.16 vs 3.72, p=0.0027). Patient's satisfaction with the diet showed a higher proportion of patients in the LRD group rated the procedure easy(12%) and fair (78.7 %) compared to CLD group (3% and 72% respectively, p=0.0178). Likewise, in terms of willingness to repeat the procedure, patients who said yes is significantly higher for low residue diet group (93%) as compared to only 81.3% for Clear liquid diet group. On the other hand, among patients with Diabetes Mellitus, Chronic

Kidney Disease, and Chronic liver disease showed no significant difference between the two groups in terms of symptoms, hunger score, satisfaction with diet and willingness to repeat procedure.(Table 3b-3d).

Table 3e showed that among elderly patients, proportion of patients with abdominal pain(37%) was higher for Clear liquid diet group compared to LRD group (12%, p=0.0343). Finally, in terms of willingness to repeat the procedure, elderly patients who said yes is significantly higher for low residue diet group (93.5%) as compared to only (81.5%) for Clear liquid diet group.

Table 3a Patients Tolerability (Gastrointestinal Symptoms)

	Low Residue Diet (n=75)	Clear Liquid Diet (n=75)	p value
GI Symptoms			
Nausea/Vomiting,n,%	4 (5.3)	9 (12.0)	0.1481 ^{ns}
Abdominal Pain/Cramping/Discomfort, n, %	12 (16.0)	26 (34.7)	0.0088*
Bloatedness,n,%	20 (26.7)	33 (44.0)	0.0269*
Hunger Score, mean±sd	4.16 ± 0.81	3.72 ± 0.95	0.0027*
Satisfaction with Diet, n, %			
Easy	9 (12.0)	3 (4.0)	
Fair	59 (78.7)	54 (72.0)	0.0178*
Difficult	7 (9.3)	18 (24.0)	
Willingness to Repeat Procedure, n, %			
Yes	70 (93.3)	61 (81.3)	0.0277*
No	5 (6.7)	14 (18.7)	0.0277*

Table 3b Patients Tolerability (Gastrointestinal Symptoms) for DM

	Low Residue Diet (n=32)	Clear Liquid Diet (n=29)	p value
--	----------------------------	-----------------------------	---------

GI Symptoms			
Nausea/Vomiting,n,%	2 (6.2)	5 (17.2)	0.1822 ns
Abdominal Pain/Cramping/Discomfort, n, %	7 (21.9)	12 (41.4)	0.1033 ns

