From a patient standpoint, bowel preparation remains the biggest deterrent to an elective colonoscopy examination. Bowel preparations are generally poorly tolerated, which results in an important impediment to colorectal cancer screening and surveillance. Tolerability, often measured in clinical trials with "willingness to retake the preparation" or with respect to taste of the purgative solution, involves other factors that may lead to negative patient assessment. These include various dietary modifications or restrictions and important adjustments in work or social schedule that may affect the pre-procedural quality of life and directly influence adherence.

Overall, patient's tolerability and satisfaction were better in the LRD group than the CLD group. The present study showed that the proportion of patients having abdominal pain/cramping/discomfort and bloatedness are significantly lower in LRD group compared to CLD group. In addition, the proportion of patients in the LRD group was less hungry before colonoscopy as compared to CLD group. Our study also showed a higher proportion of patients in the LRD group rated the procedure easy and fair compared to CLD group. These results were parallel to other studies.

However, in our subgroup analysis, no difference was found among diabetics, chronic kidney disease and chronic liver disease patients when the two groups were compared with regards to patient's tolerability and satisfaction.

The present study has some limitations. It is a single-center study with arelatively small sample size. In addition, another limitation of the study is the sample size included in the chronic kidney disease(total of 17) and chronic liver disease(10) were small compared to elderly population(116) and diabetics(61),hence we cannot totally assessed their impact on the adequacy of bowel preparation.

Conclusion

Patients on a low residue diet for bowel preparation achieved an adequate bowel preparation that is non-inferior to patients on a clear liquid diet. Furthermore, the study showed that patients tolerability and overall satisfaction were better on the low residue diet group. Patients

in the LRD group would be more willing to repeat the same bowel regimen as compared to CLD group. However, the study also showed no statistical significance on patient's tolerability and satisfaction among diabetics, chronic kidney disease and chronic liver disease patients.

REFERENCES:

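### The Discussion and Conclusion answer the four-group tolerability objective from the three groups without a significant result and leave out the elderly, 116 of 150 patients

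*Protocol*

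**What the plan says.** Under Objectives, the specific objective is "To determine the tolerability of low residue diet for colonoscopy bowel preparation in special populations (elderly, diabetes mellitus, chronic kidney disase, chronic liver disease) versus" the clear liquid diet. The Statistical Analysis section sets one rule for all comparisons: "All significant test will be done at 5 % level". It mentions no adjustment for the number of outcomes or subgroups.

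The Results text on tolerance says that diabetes, CKD and chronic liver disease showed no significant difference in symptoms, hunger, satisfaction or willingness to repeat. It then describes two elderly findings. On pain, "Table 3e showed that among elderly patients, proportion of patients with abdominal pain(37%) was higher for Clear liquid diet group"; on willingness, "elderly patients who said yes is significantly higher for low residue diet group (93.5%) as compared to only (81.5%) for Clear liquid diet group". Table 3e gives all six elderly outcomes.

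The Discussion's subgroup paragraph says "in our subgroup analysis, no difference was found among diabetics, chronic kidney disease and chronic liver disease patients" for tolerability and satisfaction. The limitations paragraph then says that the CKD and liver groups "were small compared to elderly population(116) and diabetics(61" patients), but ties that caution to adequacy of bowel preparation, not to tolerability. The Conclusion says overall tolerability and satisfaction were better on the low residue diet, then adds "However, the study also showed no statistical significance on patient's tolerability and satisfaction among diabetics, chronic kidney disease and chronic liver disease patients".

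**The concern.** The objective names four groups. The two sections that readers use for the answer report three, and these are exactly the groups with no starred result. The omitted group is the largest and the only one with starred results. A reader who wants to know about special populations sees only the null findings, introduced by a contrast with the favourable overall result.

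The Discussion also words non-significance as absence of difference, in groups of 61, 17 and 10 patients. At those sizes a test can easily miss a difference as large as the overall one. What is at stake is the reported answer to the specific objective: as written, it follows which side of p=0.05 each group fell on, not the estimated differences.

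**Working it through.** **Inputs.** Table 3e (elderly, 62 low residue v 54 clear liquid), Table 3b (diabetes, 32 v 29) and Table 3a (all, 75 v 75). Elderly share: 116/150 = 77.3%.

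**Step 1: reproduce the elderly p values.** The printed values match a two-sided Pearson chi-square multiplied by (N-1)/N.
- Pain, 12/62 v 20/54: 4.517 x 115/116 = 4.478, p=0.0343 (printed 0.0343). The count 20 is an assumption; see step 4.
- Willing to repeat, 58/62 v 44/54: 3.960 x 115/116 = 3.926, p=0.0475 (printed 0.0475).
- Nausea/vomiting: p=0.0832, as printed. Bloatedness: p=0.0845, as printed.
- Hunger: pooled SD = sqrt[(61 x 0.83² + 53 x 1.06²)/114] = 0.944; SE = 0.944 x sqrt(1/62 + 1/54) = 0.176; t = 0.38/0.176 = 2.16; p=0.033, or 0.036 by Welch (printed 0.0345, consistent with rounding).
- Satisfaction, easy/fair/difficult 6/50/6 v 3/38/13: chi-square 4.69 on 2 df, p=0.096 (printed 0.0845, the same figure as the bloatedness row).

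**Step 2: differences, low residue minus clear liquid.** For proportions, the Wald 95% CI is d ± 1.96 x sqrt[p1(1-p1)/n1 + p2(1-p2)/n2]. Elderly pain: 19.35% - 37.04% = -17.7 points, SE 8.27, CI -33.9 to -1.5. The others follow in the same way; hunger uses the pooled t interval. A higher hunger score means less hungry.

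| Outcome | Elderly (95% CI) | Diabetes (95% CI) | All |
|---|---|---|---|
| Abdominal pain | -17.7 (-33.9 to -1.5) | -19.5 (-42.5 to +3.4) | -18.7 |
| Unwilling to repeat | -12.1 (-24.1 to -0.04) | -14.8 (-33.3 to +3.8) | -12.0 |
| Bloatedness | -15.7 (-33.2 to +1.9) | -23.9 (-48.1 to +0.3), if 16/29 | -17.3 |
| Nausea/vomiting | -10.2 (-21.9 to +1.5) | -11.0 (-27.1 to +5.1) | -6.7 |
| Hunger score | +0.38 (0.03 to 0.73) | +0.46 (-0.02 to +0.94) | +0.44 |
| Rated difficult (one level of three) | -14.4 | -11.6 | -14.7 |

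The last row shows direction only and carries no interval, because the document tests satisfaction on three levels and finds it non-significant in both subgroups.

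All six elderly outcomes favour the low residue diet, and so do all six in diabetics. The diabetic point estimates are as large as the elderly ones or larger, except for the difficult rating. Their intervals are wider because n is 61 instead of 116.

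CKD and liver disease are too small to read either way. In CKD, bloatedness runs in the other direction (3/11 v 1/6), and the hunger difference of +0.27 has a CI of -0.53 to +1.07.

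**Step 3: how firm are the starred elderly results?** Willingness is p=0.084 by Fisher and 0.088 with Yates' correction; its Newcombe interval, -25.0 to +0.06 points, includes zero. Pain is p=0.039 by Fisher and 0.055 with Yates' correction. None of the three meets Bonferroni over six outcomes (0.05/6 = 0.0083). No interaction test is reported.

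**Step 4: entries that do not agree.**
- Elderly clear-liquid pain is printed as 34 with 37.0%. 34/54 = 63.0%, and 34 exceeds the whole-arm count of 26 in Table 3a. 20/54 gives both 37.0% and p=0.0343.
- The Results text gives 12% for elderly pain on the low residue diet. Table 3e has 12 patients, 12/62 = 19.4%.
- Diabetic clear-liquid bloatedness is printed as 13 with 55.2%. 13/29 = 44.8%; 16/29 gives both 55.2% and the printed p=0.0613. With 13/29 the difference in the table would be -13.6.
- Liver disease, clear-liquid satisfaction: 0 + 3 + 0 = 3 of 5 patients. The printed p=0.4444 is what Fisher gives for 5/0 v 3/2.

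**The case against.** The strongest defence is that the Conclusion's sentence is accurate. It names three groups, and none has a starred result. It does not say that special populations as a whole gain nothing, and the elderly are not listed among the exceptions to the favourable overall result. This stands: a reader might infer a general null for special populations, but the text does not state one.

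Nor is anything withheld. The Results describe two of the three starred elderly outcomes and Table 3e prints all six. A reader might suspect concealment; the documents do not support that. Only the starred hunger result is missing from the prose, and the non-significant rows are legible in the table.

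A third argument is that keeping fragile, unadjusted subgroup p values out of a Conclusion is sound caution. Step 3 shows the fragility is real. But the same caution was not applied to the three non-significant groups, which did reach the Conclusion. Caution would mean treating all four groups alike.

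Finally, the elderly are 77% of the sample and largely repeat the overall result. That is correct, and it rules out another tempting reading: that the elderly benefit where diabetics do not. The two groups' estimates are similar, so a fix that gave intervals for the elderly alone would replace one misleading contrast with another.

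**Conclusion.** The concern holds in this limited form. The specific objective covers four groups; the Discussion and Conclusion answer it for the three without a significant result and omit 116 of 150 patients, whose six outcomes all favour the low residue diet. Five of the six elderly differences are close to the overall ones; nausea/vomiting is larger (-10.2 against -6.7 points). The Discussion also presents non-significance in small groups as no difference, although the diabetic estimates match the elderly ones.

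The documents do not support a finding of hidden data, a false Conclusion sentence or an elderly-specific benefit. The overall tolerability conclusion is unaffected. The pain figures assume 20/54 and the diabetic bloatedness figures assume 16/29; both are inferred from the printed percentages and p values and need confirmation from source. The Wald intervals are approximate, and the elderly willingness interval excludes zero only by a hair.

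**What to change.** 1. Reconcile against source the four entries in step 4 and the elderly satisfaction p value (0.0845 printed, 0.096 recomputed).
2. Rewrite the Discussion's subgroup paragraph and the last Conclusion sentence to cover all four groups. For each symptom, hunger and willingness, give the low residue minus clear liquid difference with its 95% CI, labelled exploratory and unadjusted for multiplicity. Use a score-type or exact interval where cells are small or zero. Keep satisfaction as the three-level outcome that the document tests.
3. State that the elderly and diabetic differences are similar to the overall result, that CKD (17) and chronic liver disease (10) are too small for a conclusion, and that no elderly-specific benefit is claimed.
4. Replace the Discussion's no-difference wording with wording that does not read non-significance as equivalence, such as: differences were estimated too imprecisely to confirm or exclude an effect of the overall size.
5. Add the elderly hunger result (+0.38, 95% CI 0.03 to 0.73, p=0.0345) to the Results text.

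The cost is a source check of a few cells and a rewrite of three short passages from existing tables. The drawback is a less clear-cut closing statement, because several elderly intervals barely exclude zero and the diabetic ones include it.
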